3.5.15 Dabrafenib-Trametinib Dose Modification for **Pneumonitis**

Pneumonitis has been observed in patients receiving trametinib in combination with dabrafenib. To reduce the risk of pneumonitis, patients will be monitored closely for symptoms, evaluated with imaging and functional tests when appropriate.

Rev. 8/15

Dabrafenib-Trametinib Treatment Modification for Pneumonitis		
CTCAE Grade	Adverse Event Management	Action and Dose Modification
Grade 1	
 
• CT scan (high-resolution with lung windows) recommended.
 
• Clinical evaluation and laboratory work-up for infection
 
• Monitoring of oxygenation via pulse-oximetry recommended
 
• Consultation with pulmonologist recommended
 
	
 
• Continue study therapy at current dose
 

Grade 2	
 
• CT scan (high-resolution with lung windows) recommended.
 
• Clinical evaluation and laboratory work-up for infection
 
• Consult pulmonologist
 
• Pulmonary function tests – if < normal, repeat every 8 weeks until ≥ normal
 
• Bronchoscopy with biopsy and/or BAL recommended
 
• Symptomatic therapy including corticosteroids if clinically indicated
 
	
 
• Interrupt trametinib until recovery to grade ≤ 1
 
• Restart trametinib reduced by one dose level
 
• Escalation to previous dose level after 4 weeks may be considered after consultation with the subprotocol Study Chair.
 
• If no recovery to grade ≤ 1 within 2 weeks, permanently discontinue trametinib.
 

Grade 3	
 
• Same as grade 2
 
	
 
• Interrupt trametinib until recovery to grade ≤ 1
 
• Resumption of trametinib at one dose level reduction may be considered after consultation with the subprotocol Study Chair.
 
• If no recovery to grade ≤ 1 within 2 weeks, permanently discontinue trametinib.
 

Grade 4	
 
• Same as grade 2
 
	
 
• Permanently discontinue trametinib.
 

Rev. 12/16

3.5.16 Dabrafenib-Trametinib Dose Modification for Liver Chemistry Changes

Dabrafenib-Trametinib Dose Modification for Liver Chemistry Changes	
Event	Treatment modifications and assessment/monitoring

 
ALT <math>\geq</math> 3x ULN but <math><</math> 5x ULN and TB <math><</math> 2x ULN, without symptoms considered related to liver injury or hypersensitivity and who can be monitored weekly for 4 weeks
 
	
 
May continue study treatment.
 
Report as SAE if CTEP-AERS reporting criteria is met.
 
If liver chemistry stopping criteria are met any time, proceed as described below.
 
 
MONITORING: Repeat LFT (ALT, AST, ALK, bilirubin) until they return to normal/baseline or stabilise (LFT may be every 2 weeks after 4 weeks if ALT <math><</math> 3x ULN and TB <math><</math> 2 ULN). If baseline ALT and Tbili already meet these criteria, then monitoring is required only if ALT or TB rises after initiation of study therapy.


Criteria for discontinuing study drug: When any of the liver stopping criteria below is met, discontinue trametinib and dabrafenib
 
 
ALT <math>\geq</math> 3xULN and bilirubin <math>\geq</math> 2x ULN or <math>></math> 35% direct bilirubin
 
ALT <math>\geq</math> 3xULN and INR <math>></math>1.5, if INR measured (INR threshold does not apply if subject is on anticoagulant)
 
ALT <math>\geq</math> 5x ULN
 
ALT <math>\geq</math> 3x ULN persists for <math>\geq</math>4 weeks. However, if ALT was elevated 3-5x at baseline due to liver mets, then this criteria should not be used for treatment discontinuation UNLESS the ALT improves to <math><</math> 3x ULN and then subsequently rises
 
ALT <math>\geq</math> 3x ULN and cannot be monitored weekly for 4 weeks. However, if ALT was elevated 3-5x at baseline due to liver mets, then this criteria should not be used for treatment discontinuation UNLESS the ALT improves to <math><</math> 3x ULN and then subsequently rises.
 
ALT <math>\geq</math> 3x ULN associated with symptoms (new or worsening) believed to be related to liver injury or hypersensitivity
 
	
 
Immediately discontinue study treatment.
 
Do not restart/rechallenge unless approved by the subprotocol Study Chair.
 
Report as SAE if: 1) CTEP-AERS reporting criteria are met, or 2) patients meet criteria 1-2.
 
Perform liver event ASSESSMENT AND WORKUP (see below).
 
Monitor the subject until liver chemistries resolve, stabilize, or return to baseline (see MONITORING below).
 
 
If applicable, provide details on required follow up assessments (e.g., follow up for overall survival or disease recurrence or progression).
 
MONITORING: In patients stopping for criteria 1-2 (with abnormal TB and INR, indicating potentially more significant liver toxicities):
 
 
Repeat liver chemistries (ALT, AST, ALK, bilirubin) and perform liver event follow-up assessments within 24 hours.
 
Monitor subjects twice weekly until LFT return to normal/baseline or stabilize.
 
A specialist or hepatology consultation is recommended.
 
 
In patients stopping for criteria 2-6:
 
 
Repeat LFT and perform liver event follow up assessments within 24-72 hours
 
Monitor subjects weekly until LFTs return to normal/baseline or stabilize.
 
 
ASSESSMENT and WORKUP:
 
 
Viral hepatitis serology.
 
Serum CPK and LDH.
 
Fractionate bilirubin, if total bilirubin <math>\geq</math> 2x ULN.
 
CBC with differential to assess eosinophilia.
 
Record clinical symptoms of liver injury, or hypersensitivity on AE CRF.
 
Record concomitant medications (including acetaminophen, herbal remedies, other over the counter medications).
 
Record alcohol use.
 
 
Additional work up for patient stopping for criteria 1-2 (with abnormal TB and INR, indicating potentially more significant liver toxicities):
 
 
Anti-nuclear antibody, anti-smooth muscle antibody, Type 1 anti-liver kidney microsomal antibodies, and quantitative total immunoglobulin G (IgG or gamma globulins).
 
Serum acetaminophen adduct HPLC assay (in subjects with likely acetaminophen use in the preceding).
 
If there is underlying chronic hepatitis B (e.g. positive hepatitis B surface antigen): quantitative hepatitis B DNA and hepatitis delta antibody.
 
Liver imaging (ultrasound, MRI, CT) and /or liver biopsy.
 


Rev. 8/15

Footnotes:

1. Serum bilirubin fractionation should be performed if testing is available. If serum bilirubin fractionation testing is unavailable, record presence of detectable urinary bilirubin on dipstick, which indicates direct bilirubin elevations and suggesting liver injury.
2. All events of ALT  $\geq$  3xULN and bilirubin  $\geq$  2xULN (> 35% direct bilirubin) or ALT  $\geq$  3x ULN and INR > 1.5 (if INR measured) may indicate severe liver injury (possible "Hy's Law"). INR measurement is not required, and the threshold value stated will not apply to subjects receiving anticoagulants.
3. New or worsening symptoms believed to be related to liver injury (such as fatigue, nausea, vomiting, right upper quadrant pain or tenderness, or jaundice) or believed to be related to hypersensitivity (such as fever, rash or eosinophilia)
4. Includes: Hepatitis A IgM antibody; Hepatitis B surface antigen and Hepatitis B Core Antibody (IgM); Hepatitis C RNA; Cytomegalovirus IgM antibody; Epstein-Barr viral capsid antigen IgM antibody (or if unavailable, obtain heterophile antibody or monospot testing); Hepatitis E IgM antibody
5. If hepatitis delta antibody assay cannot be performed, it can be replaced with a PCR of hepatitis D RNA virus (where needed) (Le Gal *et al.*, 2005).

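### Section 3.5.16 places liver stopping criterion 2 under two overlapping monitoring schedules; the second heading should read criteria 3-6

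*Protocol*

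**What the plan says.** The liver chemistry table in Protocol section 3.5.16 numbers six criteria for stopping both drugs. Criterion 1 combines ALT at or above 3xULN with raised bilirubin. Criterion 2 combines ALT at or above 3xULN with INR above 1.5, if INR was measured. Criteria 3 to 6 rest on ALT alone, on its persistence, on whether weekly monitoring is possible, or on accompanying symptoms.

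The monitoring text then has two headings:

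- The first reads "In patients stopping for criteria 1-2 (with abnormal TB and INR, indicating potentially more significant liver toxicities". Under it the chemistries are due again inside one day, and the rule for later checks is "Monitor subjects twice weekly until LFT return to normal/baseline or stabilize". Referral to a liver specialist is advised as well.
- The second reads "In patients stopping for criteria 2-6". Its limit for the first recheck is looser: "Repeat LFT and perform liver event follow up assessments within 24-72 hours". Later checks drop to one per week, and no consultation is mentioned.

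The same table has this reporting rule: "Report as SAE if: 1) CTEP-AERS reporting criteria are met, or 2) patients meet criteria 1-2". It also has an additional work-up reserved for criteria 1 and 2. Footnote 2, attached to those two criteria, says that such events may signal severe liver injury and refers to Hy's Law.

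**The concern.** Criterion 2 appears under both headings, and nothing in the table says which one governs. A site that takes the second heading as the operative line would put a patient whom the protocol flags as possible Hy's Law on the lighter follow-up. The overlap also blurs what counts as a deviation: a recheck at 60 hours satisfies one line and breaches the other. This is an operative safety instruction, so the cross-reference should be right even though no endpoint, sample size or analysis depends on it.

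**Working it through.** The plan gives no figure to reproduce. The check compares the two groups as sets and then compares their schedules.

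**Step 1. Overlap.** The first heading covers {1, 2} and the second covers {2, 3, 4, 5, 6}. Their intersection is {2}, so criterion 2 is the only one with two schedules.

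**Step 2. The two schedules for criterion 2 (section 3.5.16).**

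| Item | Criteria 1-2 | Criteria 2-6 | Difference |
|---|---|---|---|
| Latest first repeat | 24 hours | 72 hours | 72 − 24 = 48 hours; 72 / 24 = 3 times the limit |
| Checks per week | 2 | 1 | 1 / 2 = 0.5 |
| Specialist or hepatology consultation | recommended | not mentioned | line absent |

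Both schedules run until values normalise or stabilise, so the factor of 0.5 does not depend on how long monitoring lasts.

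**Step 3. Where criterion 2 belongs.** It is paired with criterion 1 everywhere else that matters:

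- The first monitoring heading describes its group by abnormal bilirubin and INR. Criterion 2 is the only criterion that uses INR.
- The SAE reporting rule names criteria 1 and 2 together.
- The additional work-up names criteria 1 and 2 together.
- Footnote 2 treats both as possible Hy's Law.
- Section 3.2.1 makes the ALT-with-bilirubin and ALT-with-INR events the only liver events that need an initial report within 24 hours.

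**Step 4. Which heading to change.** Two single-heading repairs remove the overlap. Reducing the first heading to criterion 1 alone gives {1} and {2, 3, 4, 5, 6}, but conflicts with every item in Step 3. Starting the second heading at 3 gives {1, 2} and {3, 4, 5, 6}: the intersection is empty, the union is all six criteria, and every item in Step 3 is respected.

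**Step 5. Can both schedules be met as printed?** Yes. A repeat at 24 hours satisfies both limits, and twice-weekly checks include a weekly check.

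**Step 6. What does not depend on the overlap.** Under any criterion both drugs stop, and rechallenge needs the subprotocol Study Chair's approval. The additional work-up is tied to criteria 1 and 2 under its own heading. Section 3.2.1 uses INR at or above 1.5, so every patient with INR above 1.5 is inside the expedited rule.

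**The case against.** The strongest reply is that this is an overlapping cross-reference and not a true conflict. A site can satisfy both headings by following the first, and the section's own grouping shows which was meant. That stands, and it is the main reason the point is minor. It does not remove the point, because the table has no rule that the stricter line prevails.

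The second reply is that exposure is small. That also stands:

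- Footnote 2 says INR need not be measured and exempts patients on anticoagulants.
- The section 4.1 calendar schedules PT/INR only before registration, so criterion 2 can arise only from an INR taken outside the calendar.
- The overlap matters only when criterion 1 is not also met.
- Section 1.9 closes accrual on December 31, 2022, while the adverse event list in section 3.3 is dated July 25, 2025. Under this version, only patients still on treatment could be affected. Their number is not given.

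Third, weekly checks are not careless in themselves: the protocol chooses them after stopping for criterion 3, ALT at or above 5xULN. So the 48 hours and the halving describe the gap between two printed schedules. They do not measure harm.

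A reader might go further and infer that a possible Hy's Law patient could stay on drug, go unreported or miss the work-up. The documents do not support that, as Step 6 of the working shows.

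**Conclusion.** The point holds as a minor internal inconsistency. As written, criterion 2 carries two monitoring schedules, and criteria 3-6 is the reading that fits the rest of section 3.5.16 and section 3.2.1. The protocol does not itself print 3-6; that rests on the consistent pairing of criteria 1 and 2.

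The size is limited to follow-up after stopping in patients who meet criterion 2 without criterion 1. If a site used the second heading alone, the first repeat could come up to 48 hours later, checks would be halved, and the consultation recommendation would be missed. The protocol gives no frequency for criterion 2, so no number of affected patients can be stated.

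A reader might also infer that the bilirubin and INR wording should be harmonised at the same time, since criterion 1 and section 3.2.1 join the direct-bilirubin condition with an or, footnote 2 puts it in parentheses, and the INR operator differs between 3.2.1 and 3.5.16. The documents do not support treating that as part of this correction. Requiring both bilirubin conditions would narrow a stopping rule and an expedited-reporting rule, and changing the INR operator would move a threshold. Those are clinical decisions, and the overlap does not depend on them.

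**What to change.** In the monitoring text of the section 3.5.16 table, change the second heading from criteria 2-6 to criteria 3-6. Leave the bilirubin and INR thresholds in 3.2.1 and 3.5.16 unchanged. The cost is one digit, which can go into any further revision of the protocol. It changes no data collection, scheduled visit or analysis.

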### 3.5.17 Dabrafenib-Trametinib Dose Modification for Venous Thromboembolism (VTE)

Event	Dabrafenib	Trametinib (When Used in Combination)
Uncomplicated DVT or PE	Do not modify the dose.	Withhold trametinib for up to 2 weeks. 
 
• If improved to Grade 0-1, resume at a lower dose level.
 
• If not improved, permanently discontinue.
 

Life Threatening PE	Permanently discontinue dabrafenib	Permanently discontinue trametinib.

### 3.6 General Concomitant Medication and Supportive Care Guidelines

All supportive measures consistent with optimal patient care will be given throughout the study.

Subjects should receive full supportive care during the study, including transfusions of blood and blood products, and treatment with antibiotics, anti-emetics, anti-diarrheals, and analgesics, and other care as deemed appropriate, and in accordance with their institutional guidelines. Use of anticoagulants such as warfarin is permitted however, caution should be exercised and additional International Normalized Ratio (INR) monitoring is recommended when dabrafenib is used concomitantly with warfarin.

Radiation skin injury has been reported with concurrent use of dabrafenib and radiation. If radiation therapy is permitted on protocol, it is recommended that dabrafenib be held for 7 days before and 2 days after XRT in subjects. Because there is a potential for interaction of trametinib and dabrafenib with other concomitantly administered drugs through the cytochrome P450 system, the case report form must capture the concurrent use of all other drugs, over-the-counter medications, or alternative therapies. The Principal Investigator should be alerted if the patient is taking any agent known to affect or with the potential to affect selected CYP450 isoenzymes.

3.7 Duration of Agent-specific treatment

In the absence of treatment delays due to adverse event(s), treatment may continue until one of the following criteria applies:

- Extraordinary Medical Circumstances: If at any time the constraints of this protocol are detrimental to the patient's health, protocol treatment should be discontinued. In this event submit forms according to the instructions in the MATCH Forms Packet.
- Patient withdraws consent.
- Patient experiences unacceptable toxicity.
- Non-protocol therapies are administered.
- Disease progression

3.8 Duration of Follow-Up

Refer to the MATCH Master Protocol for specifics on the duration of follow-up.

Rev. 12/16 **4. Study Parameters**

Rev.2/16 4.1 Therapeutic Parameters for Dabrafenib plus Trametinib Treatment

**NOTE:** In addition to the study parameters listed in the MATCH Master Protocol at Step 0, the below parameters must also be performed for patients receiving Dabrafenib plus Trametinib treatment.

**NOTE:** All assessments required prior to registration to treatment should be done ≤ 4 weeks prior to registration to Steps 1, 3, 5, 7, excluding the radiologic evaluation and electrocardiogram (ECG).

Test/Assessment	Prior to Registration to Treatment	Treatment		End of Treatment	Follow Up F
		Every Cycle, prior to treatment	Every 2 Cycles		
H&P, Weight, Vital signs A	X	X J			X
Performance status	X	X J			X
CBC w/diff, plts B	X	X J			X
Serum chemistry B	X	X J			X
PT/INR and PTT	X				
Radiologic evaluation D	X		X D		X F
β-HCG C	X				
Toxicity Assessment G		X		X	X F
Pill Count/Diary H		X		X	
ECG K,L	X	X L			
Echocardiogram or Nuclear Study L	X	X L			
Dermatologic Exam M	X		X M	X	X M
Eye Exam	X	X I			
Tumor biopsy and blood sample for MATCH Master Protocol E			X	X	

A. History and physical, including vital signs and weight at the start of each cycle (up to 3 days before start of new cycle).

Rev. 8/15, 2/16 B. Albumin, alkaline phosphatase, total bilirubin, bicarbonate, BUN, calcium, creatinine, glucose, phosphorus, potassium, SGOT[AST], SGPT[ALT], sodium, magnesium, and serum tumor markers (including LDH, PSA if appropriate). For eligibility purposes, participants with creatinine levels above institutional normal, Cockcroft-Gault will be used to calculate creatinine clearance. CBC w/diff, platelets and serum chemistries should be performed on cycle 1, day 1 (or up to 7 days prior), and at the start of each subsequent cycle (up to 3 days before start of new cycle). CBC with

differential will be performed more frequently in patients with grade 4 neutropenia or thrombocytopenia until resolution to  $\leq$  grade 3. CBC and serum chemistries are only required in follow-up until values return to pre-treatment levels or until progressive disease.

- Rev. 2/16  
Rev. Add29  
Rev. 2/16
- C. Blood pregnancy test (patients of childbearing potential) required prior to beginning treatment.
- D. Disease measurements are repeated every 2 cycles for the first 26 cycles, and every 3 cycles thereafter until PD or start of another MATCH treatment step. The baseline evaluation should be performed as closely as possible to the beginning of treatment and never more than 6 weeks before registration to treatment step. For multiple myeloma patients, please refer to Section 6.4 of the MATCH Master Protocol for additional information on myeloma response criteria and the required disease assessments. Documentation (radiologic) must be provided for patients removed from study for progressive disease.
- Rev. 3/17  
Rev. Add13
- E. Additional blood specimens and/or biopsies are to be submitted from consenting patients per Section 9.3.2 of the MATCH Master Protocol. Submit at the following time points, as applicable:
- Blood specimens are to be submitted at the end of Cycle 2 (prior to start of Cycle 3 treatment). If patient progresses or treatment is discontinued prior to Cycle 3, collect the blood at that time instead. On-treatment kits for blood sample collections will be automatically shipped to sites upon registration to the treatment step.
  - Screening biopsies for additional aMOI assessments after registration to appropriate screening step, if applicable (Step 2 or Step 4).
  - At end of all MATCH study treatments, blood specimens and/or research biopsy after consent and registration to Step 8
- Please refer to Section 4 of the MATCH Master Protocol to determine whether the patient proceeds to the next screening step or to follow-up (with a potential end of treatment biopsy for research purposes on Step 8). Samples are to be submitted as outlined in Section 9 of the MATCH Master Protocol. To order Step 2/4 Screening or Step 8 kits, complete the EAY131 Collection and Shipping Kit Order Form (See Appendix XII of the MATCH Master Protocol) and fax to [contact].
- Rev. 2/16
- F. Every 3 months if patient is < 2 years from study entry, and every 6 months for year 3. Toxicity assessments and radiologic evaluations are not required to be done during Follow Up if progression has been previously reported; however if an adverse event occurs post treatment that meets the SAE reporting requirements, it still must be reported via CTEP-AERS, even if progression has occurred.
- G. Site personnel should evaluate for toxicity and discuss treatment compliance with the patient in order to ensure the medication is taken correctly; this evaluation may be conducted by telephone or in person. The Toxicity Assessment is not required prior to Cycle 1, but is required every subsequent cycle.
- H. The pill calendar will be collected at the end of every cycle. The Pill Count/Diary is not required prior to Cycle 1, but is required every subsequent cycle.
- I. As clinically indicated.
- J. For Cycle 1, if the following tests/assessments occurred within 7 days of Day 1, they do not need to be repeated at this timepoint: H&P, Weight, Vital Signs; Performance Status; CBC w/diff, plts; Serum chemistry; Concomitant Medications.
- K. Within 8 weeks of treatment assignment.
- Rev. 8/15,  
2/16
- L. Cardiac monitoring with ECG and ECHO/nuclear study (MUGA or First Pass) is needed week 5, week 13, and every 12 weeks thereafter unless clinically indicated sooner. The same modality should be used at baseline and thereafter.
- M. Test can be done by the treating physician and should be done every 2 months during study treatment, and every 2-3 months for 6 months following discontinuation of study treatment or until initiation of other anti-neoplastic agent. Refer to Section [3.5.5](#) for further instructions.

Rev. Add13 **5. Drug Formulation and Procurement**

This information has been prepared by the ECOG-ACRIN Pharmacy and Nursing Committees.

**Availability**

NO STARTER SUPPLIES MAY BE ORDERED. Subjects must be enrolled and assigned to the treatment subprotocol prior to submitting the clinical drug request to PMB.

Drug Ordering: NCI supplied agents may be requested by eligible participating Investigators (or their authorized designee) at each participating institution. Pharmaceutical Management Branch (PMB) policy requires that drug be shipped directly to the institution where the patient is to be treated. PMB does not permit the transfer of agents between institutions (unless prior approval from PMB is obtained – see general information) The CTEP-assigned protocol number must be used for ordering all CTEP-supplied investigational agents. The eligible participating investigators at each participating institution must be registered with CTEP, DCTD through an annual submission of FDA Form 1572 (Statement of Investigator), NCI Biosketch, Agent Shipment Form, and Financial Disclosure Form (FDF). If there are several participating investigators at one institution, CTEP-supplied investigational agents for the study should be ordered under the name of one lead investigator at that institution.

Submit agent requests through the PMB Online Agent Order Processing (OAOP) application (<https://ctepcore.nci.nih.gov/OAOP>). Access to OAOP requires the establishment of a CTEP Identity and Access Management (IAM) account (<https://ctepcore.nci.nih.gov/iam/>) and the maintenance of an “active” account status, a “current” password, and an active person registration status.

